R34 DA036419: Addressing Substance Use through CVCT**PI [name]**

NCT03125915

*** Please see the following for more details and primary outcome results:

[name], T.J., Dellucci, T.V., Gupta, S., Robles, G., [name], R., [name], P., & Parsons, J.T. (2019, March). A pilot randomized trial of intervention components addressing drug use in Couples HIV Testing and Counseling (CHTC) with male couples. *AIDS and Behavior*. DOI: 10.1007/s10461-019-02455-2

Correspondence concerning this protocol should be addressed to [name], Department of Psychology, Hunter College of the City University of New York, [name]. [contact]. Email: [contact]

Document Approved: 6/15/2017

Project Summary

Two factors suggest the need for HIV prevention efforts focused on partnered young men who have sex with men (YMSM). First, HIV rates are rising in this population, which already bears a disproportionate burden of HIV infection. Second, main partnerships – rather than casual partners – account for a majority of new infections, and younger age has been associated with an increased risk of main partner transmission. Substance use remains a critical factor associated with HIV sexual transmission risk behavior. Couples based approaches to HIV testing have been developed for gay men; however, existing protocols do not include a focus on substance use. In addition, existing protocols are predicated on the assumption that members of the couple possess adequate assertive communication skills to discuss relationship agreements, which may be underutilized by YMSM.

The proposed project will develop a novel intervention to reduce substance use and sexual risk behavior among partnered YMSM through the modification of an existing Couples Voluntary HIV Testing and Counseling (CVCT) protocol originally created by Drs. [name] and [name] (co-investigators). The new intervention protocol combining Couples HIV Testing and Counseling (CHTC) with a substance use module (SUM) will be informed by qualitative data gathered from 20 HIV testing providers and existing qualitative data from 21 gay couples. In addition to the development of the novel CHTC +SUM protocol, the project will develop two brief assertive communication training (CT) videos specifically for use with partnered YMSM.

The final two years of the project are devoted to a randomized controlled trial (RCT) comparing the new CHTC+SUM to the standard CHTC protocol and testing the added efficacy of the CT component. A total of 70 couples were randomized to one of four conditions (standard

CHTC, CHTC +SUM, CHTC +CT, or CHTC +SUM and CT) in a factorial design. Follow-ups were completed online at 1-, 3-, and 6-months post-intervention.

Objectives

The purpose of the current pilot study was to test the feasibility, acceptability, and preliminary efficacy of two adjunct Couples HIV Testing and Counseling (CHTC) components: assertive communication training (CT) videos and a substance use module (SUM) module intended to facilitate a discussion around drug use and the formation of joint substance use goals. It was hypothesized that these two experimental components would significantly decrease the occurrence and severity of drug use. It was further hypothesized that these components would significantly reduce the occurrence of CAS with casual partners, a behavior which might increase HIV infection risk for the couple. Two variables relevant to intervention safety were also examined: the emergence of Intimate Partner Violence (IPV) and relationship dissolution post-intervention.

Trial Design

This study utilizes a factorial (2 X 2) randomized controlled trial (RCT) design to evaluate the efficacy of the We Test intervention components. Baseline assessment is conducted prior to randomization and the receipt of intervention (CHTC as usual, CHTC + SUM, CHTC + CT or CHTC+SUM+CT). Follow-up assessments are conducted at 1-, 3-, and 6-months post-baseline.

METHODS: Participants, Interventions and outcomes

Study setting

All study assessments and intervention sessions are conducted at the PRIDE Health Research Consortium affiliated with Hunter College of the City University of New York. PRIDE

is located centrally in Manhattan with easy access to a mass public transportation hub, linking it to the larger metropolitan area. Assessment and intervention sessions are conducted in private rooms.

Eligibility Criteria

An index approach to screening was used. One member of the couple (the index partner) completed a telephone screener, which gathered demographic and behavioral information about them and their partner. To be eligible, index participants must have reported being sexually active (engaging in oral or anal sex) with their partner in the past 90 days and also identify as being in a relationship for at least 90 days. Both partners in each couple were at least 18 years of age, cis-gender male, lived in the New York City metropolitan area, and able to communicate in English. In addition, at least one member of the couple had to be 18-29; have a negative or unknown HIV status; and use drugs in the past 30 days. Finally, couples were excluded at screening if the index partner indicated that they had “physically abused their partner” or “been physically abused by their partner.” Those men who screened eligible were asked to schedule a baseline appointment at a time they could attend with their partner.

Interventions

Couples HIV Testing and Counseling (CHTC). All participants, regardless of condition, completed a CHTC session. Completion of CHTC takes approximately 30-40 minutes and involves 8-steps: (1) Introduce CHTC and Obtain Concurrence: an introduction to CHTC process and receiving the couple’s consent; (2) Prepare for and Conduct HIV Test: explanation of the HIV test and possible results couples could receive, followed by a rapid HIV test; (3) Explore Couple’s Relationship: an exploration of the couple’s relationship to build rapport; (4) Discuss HIV Risk Concerns and Reasons for Seeking CHTC: discussion of current risks, reasons for

testing and HIV prevention strategies (i.e. condom use, PrEP use, etc.); (5) Discuss Couple's Agreement: exploration of the couple's sexual agreement and rules in regards to outside sexual partners; (6) Provide Results: results are given to the partners together as a couple and can be the same (concordant negative or positive) or different (discordant); (7) Develop Care, Treatment, and Prevention Plan Based on Result: discussion of future steps regarding HIV transmission risk prevention strategies (i.e. discussion of introducing condoms or PrEP use); and (8) Link with Follow-up Services: referrals given in light of current HIV test results (i.e. for confirmatory testing and other health services).

As part of CHTC, a rapid HIV test was administered. HIV testing was conducted using the OraQuick Advanced Rapid HIV-1/2 Antibody Test. This test uses a single drop of blood and takes 20 minutes to complete. Samples were collected in a phlebotomy room and the result was read by the research assistant conducting the assessment and provided to the CHTC tester.

Assertive Communication Training (CT) Videos. The CT video component was self-delivered. Partners viewed the videos together on an audio-equipped computer in an assessment room. The video duration was approximately 20 minutes. After viewing, the partners collaboratively completed a video recognition survey as a check of intervention receipt. In the CT videos, four male couples are depicted in separate scenes discussing HIV testing, drug use, sexual agreements, and drug use during sex. Each scene is viewed twice. Initially, the couple makes one or more communication errors. In the second viewing, the couple utilizes more effective communication skills, resulting in a more adaptive resolution. Each scene is introduced by a narrator who orients viewers to the communication errors and skills in each scene.

Substance Use Module (SUM). The SUM was administered after step 5 of CHTC and prior to the delivery of HIV-test results. The SUM was designed to be completed in 5 to 10

minutes. First, the HIV-tester asked the couple to fill in a paper calendar of the past 30 days, indicating days on which either member used drugs or alcohol. The HIV-tester then asked a series of debriefing questions designed to elicit the couples' perspective on their use, establish goals and limits for drug use, and make plans to achieve these goals.

Training of Interventionists

CHTC providers were trained by Drs. [name] and [name] following the CDC's standard training protocol. This involved a two-day didactic workshop and subsequent mock delivery of the intervention. Providers required between 4 and 8 mock sessions to achieve fidelity to the protocol. The first author reviewed each mock session and provided feedback. The first author personally reviewed all mock-training session recordings. A session check-list was developed for this study based upon the CDC's checklist for the delivery of CHTC. Providers were trained to deliver the intervention covering the content on the checklist.

Fidelity Monitoring and Supervision

Supervision of all CHTC sessions was conducted by [name]. Providers met weekly with [name] for CHTC supervision, and also had one-hour of weekly group supervision in which cases were reviewed and discussed.

Outcomes

Primary outcomes

- 1) *Drug Use Instances.* Participants reported their use of a range of illicit drugs in the 30 days prior to assessment. Drugs included: cannabis, prescription drugs, opioids, cocaine/crack, stimulants, psychedelics, and club drugs (ecstasy, ketamine, and gamma aminobutyric acid). Responses were aggregated to create a dichotomous variable indicating the use (or non-use) of any of the drugs assessed.

- 2) *Problematic Drug Use.* Assessed using the 10-item Drug Abuse Screening Test (DAST-10). Participants who indicated the use of any of the substances listed above were subsequently asked to indicate the presence or absence of 9 symptoms associated with drug use. Responses were summed to produce a count of problems. Those participants who did not indicate the use of any substances assessed were assigned a value of zero.
- 3) *Condomless Anal Sex (CAS) with Casual Partners.* Assessed using a series of survey items. Participants indicated the number of times they had sex with casual partners alone and in the presence of their main partner. Those who indicated that sex with casual partners had occurred were then asked to indicate the number of times they had insertive and receptive anal sex with a casual partner. Responses were aggregated into a single variable indicating the occurrence of any CAS with a casual partner.

Secondary Outcomes

- 1) *Depression.* Assessed using the 20-item Center for Epidemiological Studies in Depression Scale Revised (CESD-R), a revised version of the CESD scale that was used to assess depressive symptoms. The items cover all the criteria for depression indicated in the Diagnostic and Statistical Manual of Mental Disorders (DSM). Total scores were calculated as a sum of responses for all 20 questions.
- 2) *Communication Patterns.* Assessed using the 11-item Communication Patterns Questionnaire (CPQ). Participants were asked to identify their typical communication patterns during moments of relational conflict at two different time points: when an issue or problem arises and during discussion of the issue or problem. Scores for each item range from 1 (*very unlikely*) to 9 (*very likely*).

Participant Timeline

Figure 1: SPIRIT Flow of participants through randomized controlled trial.

	STUDY PERIOD				
	Enrolment	Allocation	Post-allocation	Close-out	
TIMEPOINT	$-t_1$	0	1	3	6
ENROLMENT:					
Eligibility screen	X				
Informed consent	X				
Baseline	X				
Allocation		X			
INTERVENTIONS:					
CHTC					
CHTC + SUM					
CHTC + CT					
CHTC + SUM + CT					
ASSESSMENTS:					
Demographic; HIV status; PrEP Uptake; Relationship length; Drug Use Events; Problematic Drug Use; Condomless Anal Sex with casual partner; Relationship Functioning	X	X	X	X	X
	X	X	X	X	X

Sample Size

Results were generated by Monte Carlo simulation using Mplus. All estimates were based upon 10,000 sample replications and power was defined as the percentage of randomly generated samples in which the specified parameter was statistically significant. All models specified that individuals were nested within couples. Models focused on detecting between-condition differences at any one follow-up time-point. The main effects of the two interventions

were modeled at level 2. Given the pilot nature of this RCT, no a priori hypothesis was made about the size of the interaction effect anticipated. Therefore, all analyses were conducted under the conservative assumption that the interaction effect is of equivalent size and opposite direction. In this case, there is a significant effect of one treatment only at one level of the other.

Assuming 80% of the sample endorsed drug use at baseline, a sample of 70 couples has power approximately = .60 to detect a treatment effect associated with a 10% decrease in the odds of drug use at any follow-up time point. Similarly – assuming an average DAST-10 score of 2.0 at baseline – the study had power $\geq .60$ to detect a 0.5 SD difference in DAST-10 scores at any follow-up time point. CAS with casual partners and concurrent CAS with casual and main partners were both reported by approximately 26% of the sample at baseline. Under the most conservative default assumptions about the size and direction of the interaction term, this study has power approximately = 0.40 to detect a main effect associated with a 15% decrease in the odds of these variables. Under somewhat less conservative assumptions, assuming a null interaction effect, power to detect a treatment effect of this size was largely unchanged.

Recruitment

Eligible participants were recruited through a variety of online and outreach-based methods in the New York City area between January 2016 and August 2017, follow-up assessments continued through February 2018. Online recruitment efforts included the distribution of study information via listservs as well as websites and smartphone applications targeting YMSM. Outreach strategies included study staff attendance at community and social events frequented by YMSM in the New York City area.

An index approach to screening was used. One member of the couple (the index partner) completed a telephone screener, which gathered demographic and behavioral information about

them and their partner. To be eligible, index participants must have reported being sexually active (engaging in oral or anal sex) with their partner in the past 90 days and also identify as being in a relationship for at least 90 days. Both partners in each couple were at least 18 years of age, indicated a male sex and gender identity, lived in the New York City metropolitan area, and were able to communicate in English. In addition, at least one member of the couple had to be 18-29; have a negative or unknown HIV status; and use drugs in the past 30 days. Finally, couples were excluded at screening if the index partner indicated that they had “physically abused their partner” or “been physically abused by their partner.” Those men who screened eligible were asked to schedule a baseline appointment at a time they could attend with their partner.

METHODS: Assignment of interventions

Randomization

Participants will be randomly assigned to one of four study conditions using data provided by the index partner at screening. A stratified random assignment procedure will be implemented using Qualtrics. Stratification insures that conditions are balanced on: (1) age discrepancy: participant age difference with his partner (three years or less/ longer than two years); (2) relationship length with his main partner (two years or less/longer than two years); (3) race/ethnicity makeup of the participant and his partner e.g., both partners identify as White and non-Hispanic/one or both partners identify as non-White or Hispanic. Within each strata, assignment to condition is random.

Blinding

Participants were informed at the time of consent that they would complete CHTC regardless of condition assignment and that they may view CT videos and/or discuss drug use depending upon condition assigned. By virtue of this consent process and the nature of the

intervention themselves, participants therefore could not be blinded to whether or not a particular intervention component was completed. CHTC providers were blinded to whether or not participants view the CT video prior to the completion of CHTC. CHTC providers were instructed whether or not to administer the SUM as part of CHTC based upon condition and so inherently could not be blinded with respect to that intervention component. Assessment staff was blinded to condition at baseline because participants were not randomized until after the baseline assessment was completed.

METHODS: Data collection, management, and analyses

Data Management

Data will be collected on-site at baseline and at 1-, 3-, 6-months post-intervention to participants independently of their relationship partners at baseline. For each survey, participants received an email reminding them of consent information and containing the survey link. Participants were compensated \$30 for completion of each follow-up assessment. Compensation varied by participant presence: it was either delivered online via Amazon.com gift-card or in-person as cash. All survey instruments are administered using a Qualtrics-based CASI interface. To reduce the time required to attend the in-office baseline appointment, participants have the option of completing a portion of the baseline survey at-home online prior to the appointment through a Qualtrics link. Participants were be contacted to inform them their 1-, 3-, or 6-month follow assessment was available online and was provided a Qualtrics link to the survey. All procedures were approved by the Institutional Review Board of Hunter College of the City University of New York and study visits took place at a research center in New York City. In addition, we have set up a Data Safety Monitoring Board consisting of leading experts in YMSM

with particular specific expertise in randomized controlled trials, epidemiology statistical analysis, and clinical research broadly.

Data Analysis Plan

The success of randomization, the presence of differential attrition, and between-group differences on safety indicators (relationship dissolution and IPV) were assessed using repeated-measures Analysis of Variance (ANOVA) for continuous variables. To account for the nesting of people-within-couples, between-condition differences in categorical variables were assessed by testing differences among Estimated Marginal Means in Generalized Estimating Equation (GEE) models. Where indicated, pairwise comparisons were conducted using a Least Significance Difference (LSD) post-hoc test.

Between-condition differences in primary outcomes were tested within a Latent Growth Curve (LGC) framework in Mplus (version 8.0). For each outcome, a latent intercept and linear slope were specified with the first post-intervention follow-up as the initial time-point. Binomial distributions were specified for Drug Use; CAS with casual partners; and concurrent CAS. DAST-10 scores were modeled using a Poisson distribution. Growth factors were specified at both the individual level (to allow for variability between partners within couple) and the couple level (reflecting dyadic assignment to condition). For each outcome, the direct effect of the CT video and SUM were included along with a CT-by-SUM interaction effect. In this procedure, a significant effect of treatment on the latent intercept factor indicates the presence of a group difference at that time point. Meanwhile, a significant effect on the latent linear slope factor indicates that the trajectory over time differs between groups. Missing data were handled within the context of full-information maximum likelihood estimation.

Data Monitoring

The study protocols are approved by the research ethics board of the principal investigator's academic institution and are registered with clinicaltrials.gov ([NCT03125915](https://clinicaltrials.gov/ct2/show/NCT03125915)).

Abbreviations

CAS	Condomless Anal Sex
CHTC	Couples HIV Testing and Counseling
CT	Assertive Communication Training
PRIDE	PRIDE Health Research Consortium
PrEP	Pre-Exposure Prophylaxis
SUM	Substance Use Module
YMSM	Young men who have sex with men (ages 18-29, unless otherwise specified)

DECLARATIONS

Availability of data and material: Not applicable as this manuscript contains no data.

Competing interests: The authors declare that they have no competing interests.

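### The power stated for drug use (.60) and condomless anal sex (0.40) does not fit the effects named: 70 couples give about 0.05 to 0.07, and the two figures conflict with each other

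*Combined protocol and SAP*

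**What the plan says.** The Project Summary reports that "A total of 70 couples were randomized to one of four conditions" in a 2 x 2 factorial. All the power statements are in the Sample Size section. It says "Results were generated by Monte Carlo simulation using Mplus", and that "power was defined as the percentage of randomly generated samples in which the specified parameter was statistically significant". It gives no alpha, sidedness or within-couple correlation.

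The modelling assumptions are:
- Clustering: "All models specified that individuals were nested within couples".
- Timing: "Models focused on detecting between-condition differences at any one follow-up time-point".
- Interaction: "all analyses were conducted under the conservative assumption that the interaction effect is of equivalent size and opposite direction".

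For the binary primary outcomes it then states:
- Drug use, 80% at baseline: "power approximately = .60 to detect a treatment effect associated with a 10% decrease in the odds of drug use at any follow-up" time point.
- CAS with casual partners and concurrent CAS, each about 26% at baseline: "this study has power approximately = 0.40 to detect a main effect associated with a 15% decrease in the odds of these variables". A null interaction is said to leave this largely unchanged.

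**The concern.** Odds ratios of 0.90 and 0.85 are very small effects for 140 men in 70 couples, so power of .60 and 0.40 looks far too high. The pair also looks to be in the wrong order: the larger effect, on the outcome with more binomial variance and so more information about the log odds, is given the lower power.

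These sentences are the trial's stated sensitivity for two of its three primary outcomes. A reader of a null result would take it that the trial had a 60% or 40% chance of detecting a 10 to 15% reduction in odds. If the wording is right, that chance is close to the false-positive rate.

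**Working it through.** **Inputs from the documents.** 70 couples, so 140 men; four conditions; one follow-up at a time; baseline proportions 0.80 and 0.26; odds reductions of 10% and 15%.

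**Assumptions where the plan is silent.** Two-sided 0.05; equal allocation; control proportion at follow-up equal to baseline; no attrition, which favours the stated figures. For pairs the design effect is D = 1 + ICC, so it lies between 1 and 2 for any non-negative correlation; 1.0 to 1.5 is used below. A pooled main effect compares 70 v 70 men. Under the equal-and-opposite interaction a component acts at only one level of the other factor, which compares about 35 v 35 men.

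**Step 1: proportions implied by the wording.**
- Drug use: odds 0.80/0.20 = 4.0; 4.0 × 0.90 = 3.6; 3.6/4.6 = 0.783.
- CAS: odds 0.26/0.74 = 0.351; × 0.85 = 0.299; 0.299/1.299 = 0.230.

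**Step 2: power as worded.** With n men per arm, SE² = D × [1/(n p₀(1−p₀)) + 1/(n p₁(1−p₁))], λ = |ln OR|/SE, and power = Φ(λ − 1.96) + Φ(−λ − 1.96).
- Drug use, 70 v 70, D = 1: SE = √(0.0893 + 0.0840) = 0.416; λ = 0.105/0.416 = 0.253; power 0.057.
- CAS, 70 v 70, D = 1: SE = √(0.0743 + 0.0807) = 0.394; λ = 0.163/0.394 = 0.413; power 0.070.

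| Outcome | Stated | 35 v 35, D 1.0–1.5 | 70 v 70, D 1.0–1.5 |
|---|---|---|---|
| Drug use, OR 0.90 | .60 | 0.052–0.054 | 0.055–0.057 |
| CAS, OR 0.85 | 0.40 | 0.057–0.060 | 0.063–0.070 |

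Neither stated figure is reproduced. One-sided 0.05 gives 0.07–0.08 and 0.08–0.11. A simulation of 20,000 trials of 70 couples, with latent within-couple correlation of 0, 0.4 and 0.6, rejected in 0.04–0.05 (drug use) and 0.05–0.06 (CAS), under both the equal-and-opposite and the null interaction.

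**Step 3: what the stated powers would require.** Powers of .60 and 0.40 need λ = 2.21 and 1.71. Since n scales with λ², that is about 5,350 independent men per arm for drug use and 1,195 for CAS. Alternatively, a two-sided alpha of about 0.59 and 0.36–0.38 would be needed.

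**Step 4: the two figures against each other.** The ratio of λ is 0.413/0.253 = 1.63, and 1.63² = 2.66. A sample giving .60 for drug use would give 0.95 for CAS; one giving 0.40 for CAS would give 0.18 for drug use. For both to hold, the CAS design effect would have to be (2.21/1.71)² × 2.66, about 4.5 times that for drug use. Pairs allow at most 2.

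**Step 5: other effect scales, one time point, two-sided 0.05, D 1.0–1.5.**

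| Reading | 35 v 35 | 70 v 70 |
|---|---|---|
| Drug use 80% to 70% (10 points) | 0.12–0.16 | 0.20–0.27 |
| Drug use 80% to 72% (relative 10%) | 0.10–0.12 | 0.15–0.20 |
| CAS 26% to 11% (15 points) | 0.25–0.35 | 0.44–0.61 |
| CAS 26% to 22.1% (relative 15%) | 0.06–0.07 | 0.07–0.08 |

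A percentage-point reading brings CAS near 0.40 but leaves drug use well short of .60 (at most 0.29 in simulation). A 10-point drug-use fall reaches about .60 only by using three follow-ups as if independent, with 70 v 70 men: 1 − (1 − 0.274)³ = 0.62 for a hit at any of the three, or 0.65 with all three pooled.

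**Step 6: effects that do match the stated powers.** Power of .60 for drug use needs a fall from 80% to about 48–55% (35 v 35) or 59–63% (70 v 70). Power of 0.40 for CAS needs a fall from 26% to about 6–10% or 12–14%.

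**The case against.** **Controls may not stay at baseline.** Every arm receives couples testing and counselling, so control proportions could move. With controls at 70% drug use and 20% CAS the information ratio falls from 2.66 to 1.69, and at 60% and 15% to 1.18. Different within-couple correlations for the two outcomes could then reverse the order. This stands: the conflict between the two figures depends on control proportions near baseline and on the same contrast for both. It does not rescue the size of either figure. Even at the largest possible variance, p(1−p) = 0.25, with 70 v 70 men and D = 1, λ is at most 0.105 × √(35 × 0.25) = 0.31 for drug use and 0.163 × √(35 × 0.25) = 0.48 for CAS, giving power of about 0.06 and 0.08.

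**Sidedness is not stated.** A one-sided 0.05 test lifts the 10-point drug-use reading to as much as 0.39. The ceiling of 0.27 is therefore for two-sided testing. Both fall short of .60.

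**The analysis uses all waves.** The Data Analysis Plan fits a growth curve, and its estimate at one time point borrows from the other waves. A multi-wave model might explain .60 on a 10-point scale. But the Sample Size section describes single-time-point models and does not mention a growth model, repeated measures on the same men are unlikely to be independent, and 0.65 is reached only with no correlation at all.

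**A mislabelled scale is more likely than a wrong simulation, and this is a pilot.** Both points are fair. The simulated inputs are not in the documents, so 0.05 to 0.07 is the power for the effects as worded, not a measure of what the trial could detect. The plan also admits modest power openly. It still names particular effect sizes for primary outcomes, and those do not match the powers given.

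**Conclusion.** The concern holds. For the effects as written, power is about 0.05 to 0.07 rather than .60 and 0.40, and no plausible choice of alpha, sidedness, within-couple correlation, contrast or control proportion brings it close to either stated figure. This conclusion is firm. That the two figures contradict each other holds if control proportions stay near baseline and the same contrast is used for both outcomes. Which element is wrong, the effect scale or the power, cannot be settled from the documents. Allocation, outcomes and analysis are not affected; the fault lies in the stated sensitivity for two of the three primary outcomes.

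**What to change.** Keep 70 couples. For each binary primary outcome, state from the simulation inputs:
- the control and treated proportions and the odds ratio simulated;
- alpha and sidedness;
- the within-couple correlation or couple-level variance;
- the interaction assumption, and whether the contrast is the effect at one level of the other factor or the pooled effect;
- whether one follow-up or several entered the model.

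Then correct the effect size or the power in each sentence, whichever is wrong. The DAST-10 sentence can stay, as it is not shown to be wrong.

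The cost is two edited sentences, and a rerun of the simulation if its inputs are not on file. The stated sensitivity will look less favourable. No extra couples are needed.

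### With 17 to 18 couples per condition, the GEE tests for categorical checks and safety indicators do not reliably hold 5%, and the plan omits the settings that decide which way they err

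*Combined protocol and SAP*

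**What the plan says.** The Data Analysis Plan opens by listing what its first paragraph covers: "The success of randomization, the presence of differential attrition, and between-group differences on safety indicators (relationship dissolution and IPV"). Continuous variables go to repeated-measures ANOVA. For the rest, "between-condition differences in categorical variables were assessed by testing differences among Estimated Marginal Means in Generalized Estimating Equation (GEE) models". Follow-up is unadjusted: where indicated, "pairwise comparisons were conducted using a Least Significance Difference (LSD) post-hoc test".

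The Project Summary fixes the number of independent units: "A total of 70 couples were randomized to one of four conditions". The Objectives name the safety variables as "the emergence of Intimate Partner Violence (IPV) and relationship dissolution post-intervention". Under Eligibility Criteria, couples are screened out if the index partner reports physical abuse in either direction, so IPV may well be uncommon.

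The plan does not say whether the comparison is made on the proportion or the logit scale, whether the variance is robust or model-based, whether a small-sample correction applies, or what happens when a condition has no events. It gives no IPV or dissolution rate and no within-couple correlation.

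**The concern.** A test of GEE marginal means is normally referred to a large-sample distribution, and here the sample is couples. With about 17 or 18 per condition, the estimated variance depends strongly on the observed proportion. A condition that happens to have few events gets too small a variance and too much weight. A condition with none gets a robust variance of exactly zero and has no finite logit.

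At stake are the trial's safety comparison and its checks on randomization and attrition. One unstated setting could produce false signals of harm or of differential attrition. Another could leave almost no chance of detecting a real difference in a rare event.

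**Working it through.** The plan states no error rate for these tests, so there is no figure to reproduce. The check finds the actual size when the conditions do not differ.

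**Inputs**
- From the documents: 70 couples, 4 conditions, 2 partners per couple; CAS with casual partners about 26% at baseline; drug use assumed 80% at baseline (Sample Size).
- Assumed: equal allocation (70/4 = 17.5, so 17/17/18/18), two-sided 5%, within-couple correlation ρ of 0.3 to 1.0 (1.0 is a shared event such as dissolution), full response, and all other event rates.

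**Test on the proportion scale**
- For a condition with k couples, the marginal mean is p̂ = events/(2k). The uncorrected robust variance is v = Σ(couple residual total)²/(2k)². In 15 of 15 data sets this closed form gave the same Wald statistic as a standard GEE routine.
- The overall statistic is W = Σ(p̂ − p̄)²/v over the four conditions, with p̄ the inverse-variance weighted mean. It is compared with the chi-square (3 df) cutoff of 7.81.

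**One example, couple-level event**
- Suppose the counts are 0/17, 3/17, 2/18 and 2/18. For a shared event v = p̂(1 − p̂)/k, so the empty condition has v = 0 and pulls p̄ to 0.
- Each other condition then adds p̂²/v = kp̂/(1 − p̂): 3/(14/17) = 3.64, 2/(16/18) = 2.25, and 2.25 again.
- W = 8.14, p = 0.043: a significant difference from seven events.
- A Pearson test on the same counts has expected values 1.7, 1.7, 1.8 and 1.8. It gives 1.7²/1.53 + 1.3²/1.53 + 2 × 0.2²/1.62 = 1.89 + 1.10 + 0.05 = 3.04, p = 0.39.

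**Simulated size at nominal 5%** (40,000 null trials per setting; ranges run over ρ = 0.3 to 1.0)

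| Event rate | Proportions, all trials | Proportions, no empty condition | Logit, no empty condition | At least one empty condition |
|---|---|---|---|---|
| 5% | 2-10% | about 0% | about 0% | 63-88% |
| 10% | 15-17% | 0-3% | 0-2% | 17-50% |
| 15% | 12-17% | 2-9% | 1-3% | 3-21% |
| 20% | 11-12% | 5-10% | 1-4% | 1-8% |
| 26% | about 10% | 9-10% | 2-5% | 2% or less |
| 50% | about 9% | about 9% | 3-6% | 0% |
| 80% | 11-12% | 5-10% | 1-4% | 1-8% |

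For the 80% row, an empty condition means one in which every partner has the event.

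**Chance of an empty condition at a 5% rate**
- The probability that neither partner has the event is (1 − p)² + ρp(1 − p).
- At ρ = 1 this is 0.95, and 1 − (1 − 0.95¹⁷)²(1 − 0.95¹⁸)² = 0.88.
- At ρ = 0.3 it is 0.917, which gives 0.63.

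**Other readings of the plan**
- A single pairwise comparison runs at about 7% at most.
- A two-level comparison of 35 with 35 couples runs at about 5-7% at rates of 15% or more.
- With an empty condition, one standard GEE routine reported convergence, with a log-odds contrast of −23.6 and standard error 0.79. It gave no error.

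**The case against.** The strongest reply is that the plan names neither a Wald statistic, nor the proportion scale, nor uncorrected robust variance, nor a 3-df test. Under other choices the size is near nominal or below it. That stands: the inflation belongs to one reading. It is the literal one, because marginal means of a binary outcome on the response scale are proportions, but it is not the only one. The same fact is also the difficulty, because the error rate then depends on a software setting the plan does not record.

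It is also fair that the figures above about 12% come mainly from empty conditions, and that once these are set aside rare events make the test conservative. Empty conditions do not explain everything, though. At the documents' own 26% rate they occur in 2% of trials or fewer, and the size is still about 10%.

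Three stronger inferences are tempting and are not supported:
- **That the LSD step is further evidence of a faulty standard error.** Six unadjusted pairs among four conditions give about a 20% chance of at least one significant result even when every test is valid. That is multiplicity, and the plan limits LSD to cases where it is indicated.
- **That rare events make the test uncomputable.** The logit estimate does not exist, but software can return a meaningless one. How often this happens depends on event rates the documents do not give.
- **That the pilot's efficacy conclusion is at risk.** The primary outcomes are analysed by latent growth curve models, and no stated decision depends on these checks.

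**Conclusion.** The concern holds in limited form. The GEE comparisons are under-specified for 17 to 18 couples per condition and cannot be relied on to hold 5%.

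- As an overall Wald test on proportions with uncorrected robust variance, the size is about 9-12% at rates from 20% to 80% and about 12-17% at 10-15%.
- On the logit scale it is at or below about 5% (just under 6% at the highest setting) and close to zero for rare events, where the weakness is lack of power.
- At a 5% rate an empty condition is more likely than not, and the estimate is then undefined or spurious.

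These figures rest on equal allocation, full response and the assumed correlations. All rates except 26% (reported) and 80% (the plan's own assumption) are also assumed. The point reaches only the categorical checks and safety comparisons. It should be corrected, but it does not touch the primary analysis.

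**What to change.** For every categorical between-condition comparison in that paragraph, keep the estimated proportions but take the p-value from a permutation test. Permute condition labels over whole couples, within the randomization strata as actually used, and use the same reference for any pairwise follow-up. This matches the design ("Within each strata, assignment to condition is random"), remains defined when a condition has no events, and needs no choice of scale or covariance. In a stratified simulation it held about 3-5%. Report each difference with an exact or score-type interval on couple-level counts, and state when a couple counts as having the event if the partners' reports differ.

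The strata need to be written down first. The two age-difference categories under Randomization overlap (one is three years or less, the other longer than two years), and three binary factors give eight strata averaging 70/8 = 8.75 couples.

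A small-sample correction is simpler but only a partial remedy. Multiplying the variance by n/(n − 1) and using F(3, 66) lowers the proportion-scale test from 9.1-10.4% to 6.9-7.8% (rates 20-50%, correlation 0.3-0.5), and it does not address an empty condition.

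The cost is a few sentences in the plan and a short piece of code. P-values will be somewhat larger and discrete for rare events.
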